--------------------------	--

CONFIDENTIAL

	
If the result of the serum pregnancy test is positive, the participant will be withdrawn from the study and a Pregnancy Notification Form completed. Blood samples will be collected and shipped to nominated laboratories for preparation of serum, plasma and peripheral blood mononuclear cells (PBMCs) for use in immunological analyses.
 
Subjects will be withdrawn from the study if deemed necessary by the PI if their condition cannot be sufficiently controlled with minor adjustments in treatment. All adjustments in treatment will be recorded.

Contraindications:	Severe local or systemic reactions that preclude further administration.
Safety parameters:	Refer to Table 1
Clinical procedures / assessments:	Refer to Table 1
Specialised analyses:	T-cell responses against RA autoantigens (e.g., MHC II tetramer analyses, tetramer-stimulated analyses for intra-cellular cytokines, ELISpot analyses)
Sample size determination:	No formal sample size calculation is proposed for this clinical trial. This clinical trial is a proof-of-principle study and results from this clinical trial will be utilised for power calculations for subsequent studies.
Statistical analyses:	
Planned analyses: A statistical analysis plan (SAP) will be generated prior to database lock that describes the planned statistical analysis of the study. All data will be provided in data listings sorted by treatment group, time since baseline, and subject number. Categorical data will be summarised by the number and percent of subjects falling in each category. Continuous variables will be summarised by descriptive statistics including mean, standard deviation, median and minimum and maximum. Comparisons will be made between post-treatment and pre-treatment values in the DEN181-treated group and between DEN181-treated and placebo-treated groups. Relationships between DAS28CRPv4 and descriptive data will be determined in univariate and multivariate analyses. Multilinear regression models will assess longitudinal trends.
 
Safety will be assessed by summarising adverse events and clinical laboratory tests. Adverse events will be listed and summarised by system organ class and preferred terms (current version of MedDRA) per treatment group. Vital signs and clinical laboratory tests will be tabulated and summarised per treatment group. Adverse event severity will be graded according to NIH CTCAE Version 4.03.

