10.7 Guidance for dose modification or discontinuation of treatment

To date, no specific toxicities have been identified that result from DEN-181 treatment. Any toxicities and/or abnormal laboratory findings should be investigated for aetiology and graded according to Appendix 1.

The following toxicity management will be followed:

- Grade 1 or 2: Patients may continue study treatment/placebo (except if they have an elevated temperature of >38 degrees Celsius or inter-current systemic illness). Dosing may be delayed for up to 7 days. Any dosing delays of >7 days may require that the subject is withdrawn after discussion with the Medical Monitor. Safety assessments will occur immediately prior to each dosing of IMP;
- Grade 3: Patients with any Grade 3 toxicity considered to be at least possibly related to treatment (i.e. treatment related events) should be evaluated carefully by the Investigator prior to continuing IMP treatment. Investigators may discuss individual cases with the Medical Monitor;
- Grade 4: Patients developing any Grade 4 toxicity should have treatment interrupted. The Investigator should contact the Medical Monitor to discuss the subject’s withdrawal.

Subjects will be withdrawn from treatment permanently should any of the following occur:

- Treatment related Grade 4 toxicity
- The need to take medication which could interfere with study measurements
- Subject unwilling to proceed and/or consent is withdrawn.

Where possible subjects who are withdrawn from treatment will remain on the study and attend the scheduled study visits, provided the Investigator deems it appropriate and the Sponsor approves.

Dosing will be stopped if suspected adverse drug reactions, changes to vital signs or clinical laboratory results are observed and these changes pose a significant health risk.

A corresponding adverse event will be captured within the CRF.

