12.2 Criteria for premature withdrawal from treatment or the study

Subjects have the right to withdraw from treatment or the study at any time for any reason. The Investigator must make every reasonable effort to keep each subject in the study except where termination or withdrawal is for reasons of safety. The Investigator also has the right to withdraw patients from treatment or the study in the event of concurrent illness, AEs, pregnancy, treatment failure after a prescribed procedure, protocol violations, administrative reasons or other reasons.

It is understood by all concerned that an excessive rate of withdrawals from the study can render the study difficult to interpret; therefore, unnecessary withdrawal of subjects from the study should be avoided.

The reasons for withdrawal of the subject must be recorded on the CRF. The following are considered justifiable reasons for subject withdrawal:

- The need to take medication which may interfere with study measurements
- Intolerable/unacceptable adverse experiences
- Major violation or deviation of study protocol
- Non-compliance of subject with protocol
- Subject unwilling to proceed and/or consent is withdrawn
- Withdrawal from the study is, in the Investigator's judgement, in the subject's best interest
- Pregnancy of female study subject at any time during the study period (if applicable).

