12.3 Withdrawal of subjects from study product

Investigational medicinal product is administered once during Part A of this protocol and three times during the conduct of Part B of this protocol.

Section 10.7 provides guidance for dose modification or discontinuation of IMP in the event of AEs or abnormal laboratory values.

If a subject permanently discontinues dosing with IMP, for example as a result of an AE, every attempt should be made to keep the subject in the study and continue to perform the required study related follow-up and procedures.

The ideal is to continue to follow the subject for the full study period or until resolution of the adverse event. If it is not possible for the subject to remain in the study for the full study period, every attempt should be made to keep the subject in the study up to the Exit Evaluation at Day 57. If the subject remains in the study but off study treatment, all study procedures should continue as per protocol.

If the subject will not remain in the study for all study related procedures, the Exit Evaluation should be performed wherever possible.

All subjects who discontinue study medication dosing should be followed for at least 30 days after the last dose of IMP in order to monitor subjects for possible post-treatment events which may occur after IMP has been discontinued.

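### The synopsis, and Section 12.2 on one reading, let an uncontrolled condition end study visits and not only dosing, so later DAS28CRPv4 scores can go missing because of the outcome

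*Protocol*

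**What the plan says.** The synopsis (Study procedures) states: "Subjects will be withdrawn from the study if deemed necessary by the PI if their condition cannot be sufficiently controlled with minor adjustments in treatment". The trigger is failure to control the patient's condition, the consequence is leaving the study, and the decision is the PI's.

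Section 12.2 gives the Investigator a right to "withdraw patients from treatment or the study in the event of concurrent illness, AEs, pregnancy, treatment failure after a prescribed procedure", among other reasons. Its list of justifiable reasons for withdrawal includes: "The need to take medication which may interfere with study measurements". The same section also asks for retention: "The Investigator must make every reasonable effort to keep each subject in the study except where termination or withdrawal is for reasons of safety".

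Section 10.7 names almost the same medication trigger, "The need to take medication which could interfere with study measurements", but as a reason for permanent withdrawal from treatment. It continues: "Where possible subjects who are withdrawn from treatment will remain on the study and attend the scheduled study visits". Staying on visits is conditional, however, since it applies only "provided the Investigator deems it appropriate and the Sponsor approves". Section 12.3 says that when dosing stops for good, "every attempt should be made to keep the subject in the study and continue to perform the required study related follow-up". It also asks for at least 30 days of follow-up after the last dose in those who discontinue dosing, and for an Exit Evaluation where that is possible. Section 12.4 asks for a complete final evaluation at withdrawal, and Section 12.5 rules out replacement.

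Section 9.2.2 allows NSAIDs and steroids, such as joint injection or prednisone above 10 mg/day, after Day 29. Prednisone below 10 mg/day is allowed throughout.

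**The concern.** Mean change in DAS28CRPv4 is a secondary endpoint (Section 4.2.2), and the same score evaluates RA exacerbation within the primary safety endpoint (Section 4.2.1). If patients leave the study because their disease is not controlled, their later scores are missing because of the outcome being measured. Section 13.5 leaves the handling of missing values to the SAP, but that does not settle the matter: no analysis can recover scores or blood samples that were never taken. This is a rule about data collection, and it belongs in the protocol.

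Sites also receive mixed instructions. A Part B patient who flares before the Day 15 dose could be taken off the study under the synopsis, or taken off the drug and kept on visits under Sections 10.7 and 12.3.

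**Working it through.** The protocol gives no dropout rate, power calculation or DAS28CRPv4 standard deviation, so there is no planned figure to reproduce. The check compares the texts and then counts what would be lost.

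**1. The rules side by side**

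| Place | Trigger | Consequence |
|---|---|---|
| Synopsis | Condition not controlled by minor treatment adjustments | Leaves the study, at the PI's judgement |
| 12.2, right to withdraw | Treatment failure after a prescribed procedure, and others | Leaves treatment or the study |
| 12.2, list | Interfering medication | Withdrawal, kind not stated |
| 10.7 | Interfering medication | Leaves treatment; visits continue where possible, if Investigator and Sponsor agree |
| 12.3 | Permanent stop of dosing | Every attempt to continue follow-up |

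**2. Timing.** Dosing ends on Day 1 in Part A and Day 15 in Part B.
- Before the last Part B dose, the synopsis and Sections 10.7/12.3 point different ways.
- From the last dose to Day 29, no drug is left to stop, but Section 9.2.2 does not yet allow the stronger rescue. Leaving the study is then a route to treatment.
- After Day 29, rescue is allowed on study, so withdrawal is no longer needed to obtain it.

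**3. Data lost** (Table 1-1). Post-baseline DAS28CRPv4 is scored on Days 8, 15, 29 and 57 (4 scores). Post-baseline tetramer samples are taken on Days 8 and 29 (2 samples). The single evaluation on leaving is not counted.

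| Leaves after | DAS28CRPv4 lost | Tetramer lost |
|---|---|---|
| Day 8 | 3 of 4 | 1 of 2 |
| Day 15 | 2 of 4 | 1 of 2 |
| Day 29 | 1 of 4 | 0 of 2 |

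**4. What the safeguards return.** The Exit Evaluation (Section 7.3.4) includes DAS28CRPv4 and CRP but no tetramer analysis. The 30-day follow-up in Section 12.3 runs to Day 1 + 30 = Day 31 if only the first dose was given, or Day 8 + 30 = Day 38 after two. Both pass Day 29 but stop short of Day 57, even with the 7-day follow-up window (Day 50). Its stated purpose is post-treatment events, so the scheduled scores and the tetramer sample are not guaranteed.

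**5. Leverage of one patient, as illustration only.** Let p be the share of an arm lost and d the lost patients' later score minus the mean of the rest. Then full-arm mean = observed mean + p × d. The range d = -0.5 to +1.5 is an assumption. It includes negative values because a retained patient would be scored after rescue.

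| Arm | p | p × (-0.5) | p × 1.5 |
|---|---|---|---|
| Part B DEN-181 group | 1/15 = 6.7% | -0.033 | +0.100 |
| Part B placebo, pooled | 1/10 = 10% | -0.050 | +0.150 |
| Part B placebo, one group | 1/5 = 20% | -0.100 | +0.300 |
| Part A active cohort | 1/4 = 25% | -0.125 | +0.375 |

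The effect on a between-arm difference is p₁d₁ - p₀d₀, which is zero when losses and d are equal in both arms.

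**The case against.** The case for leaving the text alone has weight. The synopsis rule is discretionary and sits beside a general duty of retention. The 12.2 list does not say whether it means leaving treatment or leaving the study, so its medication item can be read in line with Section 10.7. Neither place names RA; the synopsis speaks only of the patient's condition. The flare should still appear as an adverse event and a withdrawal, and the score on leaving should be captured. Scores kept after rescue are affected by that rescue. All of this stands and lowers the weight, but the synopsis sentence still points away from Sections 10.7 and 12.3.

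Three stronger readings are tempting, and the protocol does not support them.
- A reader might infer that after the last dose the permission can only serve to end follow-up. Until Day 29 it is also a way to rescue that Section 9.2.2 does not yet allow.
- A reader might infer that 12.2 flatly contradicts 10.7. It is ambiguous, and only one reading conflicts.
- A reader might infer a sizeable bias of known direction. Larger figures can be produced: removing Day 57 scores whenever Day 29 worsening exceeds 0.6 or 1.2 (assumed SD of change 0.8 to 1.2, correlation 0.5 to 0.7) loses 7% to 31% of placebo patients and makes the placebo mean look 0.05 to 0.43 too favourable. But the protocol sets no such threshold, rescue is open after Day 29, and the simulation ignores rescue effects. Those figures should carry no weight.

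**Conclusion.** The point holds as a minor one. The synopsis, and 12.2 on one reading, allow loss of disease control to end scheduled visits, where Sections 10.7 and 12.3 would end dosing only. Section 9.2.2 makes study withdrawal the likely outcome for a patient who needs stronger rescue before Day 29. When the permission is used, the Day 57 score is lost, and for earlier leavers the Day 29 score and tetramer sample as well, for a reason tied to the outcome.

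The schedule counts rest on the protocol alone. The mean shifts rest on an assumed d and on one lost patient per arm. How often the permission would be used, and the size and direction of any bias, cannot be derived from the protocol. The endpoint is secondary, and Section 13.1 makes the study descriptive.

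**What to change.** Amend four places.
- **Synopsis sentence, the treatment-failure clause in 12.2, and the medication item in the 12.2 list:** state that an uncontrolled condition or need for interfering medication ends any remaining dosing only. Scheduled DAS28CRPv4, safety and remaining immunology visits continue to Day 57 unless the patient withdraws consent or the Investigator judges continued visits unsafe. Withdrawals for pregnancy or safety stay as they are.
- **Section 9.2.2:** allow clinically needed rescue before Day 29, require that it be recorded, and state that it stops the study drug without ending follow-up. Without this change the other three would conflict with 9.2.2.

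The cost is wording in four places and a few visits that are already scheduled. The real downside is that some DAS28CRPv4 scores and Day 29 immunology values will be post-rescue. The SAP must flag these and say how they enter the analysis.

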1 LIST OF ABBREVIATIONS

ABBREVIATION	DESCRIPTION
ACPA	Anti-Citrullinated Peptide Antibody
AE	Adverse Event
ADR	Adverse Drug Reaction
ALDH	(retin)aldehyde dehydrogenase
ALP	Alkaline Phosphatase
ALT	Alanine Transaminase
AST	Aspartate Aminotransferase
Beta-HCG	Beta Human Chorionic Gonadotropin
BMI	Body Mass Index (Weight in kg divided by height in m ²)
BP	Blood Pressure
cGMP	Current Good Manufacturing Practice
C _{max}	Observed maximum concentration
CBC	Complete Blood Count
CCP	Cyclic citrullinated peptide
CI	Confidence Interval
cit	citrullinated
CMI	Cell-mediated Immunity
CMV	cytomegalovirus
COA	Certificate of Analysis
CII	Collagen type II protein
CII Peptide	Peptide corresponding to amino acids 259 to 273 of human Collagen II with hydroxyproline in the 273 position. Amino Acid sequence: GIAGFKGEQQPKGE-Hyp
CRF	Case Report Form
CRP	C-reactive protein

ABBREVIATION	DESCRIPTION
CRO	Clinical Research Organisation
CSR	Clinical Study Report
CTN	Clinical Trial Notification
d	Day
DAS28CRPv4	Disease Activity Score for 28 joints plus CRP assessment (4variable calculation)
DBP	Diastolic Blood Pressure
DC	Dendritic Cell
EBV	Epstein-Barr Virus
ECG	Electrocardiogram
EPC	Egg Phosphatidylcholine
EPG	Egg Phosphatidylglycerol
ELISA	Enzyme-linked immunosorbent assay
ELISPOT	Enzyme-linked immunospot assay
ESR	Erythrocyte sedimentation rate
FBC	Full Blood Count
GCP	Good Clinical Practice
GGT	Gamma Glutamyltransferase
GLP	Good Laboratory Practice
GMP	Good Manufacturing Practice
HA peptide	Influenza Hemagglutinin peptide aa306-318
Hb	Haemoglobin
Hct	Haematocrit
HIV	Human Immunodeficiency virus
HED	Human Equivalent Dose
Hep B	Hepatitis B
Hep C	Hepatitis C

ABBREVIATION	DESCRIPTION
HLA-DR	An MHC class II surface receptor encoded by the human leukocyte antigen complex
HR	Heart Rate
HREC	Human Research Ethics Committee
IB	Investigator's Brochure
IFN γ	Interferon γ
ICH	International Council on Harmonisation of Technical Requirements for Registration of Pharmaceuticals for Human Use
IMP	Investigational medicinal product
Inj	Injection
IUD	Intrauterine device
ITT	Intention to Treat
LN	Lymph nodes
LFT	Liver Function Test
mcg	Microgram
MHC II	Major Histocompatibility Complex Class II
MTX	Methotrexate
NHMRC	National Health and Medical Research Council
NIH CTCAEv4.03	National Institutes of Health Common Terminology Criteria for Adverse Events v4.03
NOAEL	No Observable Adverse Effect Limit
PBMC	Peripheral blood mononuclear cells
PUVA	Psoralen and Ultraviolet A Radiation
RA	Rheumatoid Arthritis
RT	Room temperature
SAE	Serious Adverse Event
SAP	Statistical Analysis Plan

ABBREVIATION	DESCRIPTION
SC	Subcutaneous
SMC	Safety Monitoring Committee
SOC	System Organ Class
SUSAR	Serious Unexpected Serious Adverse Reaction
TEAE	Treatment Emergent Adverse Event
Teff	T effector cells
Tfh	T follicular helper
T _{max}	Time of observed maximum concentration
Treg	T regulatory cells
Trm	T resident memory
TG	transgenic
TGA	Therapeutic Goods Administration

DEN-181

Dendright Pty Ltd

3 INTRODUCTION

3.1 Disease

Rheumatoid arthritis (RA) is an incurable autoimmune disease affecting 1 in 100 adults worldwide. RA reduces survival by an average of 10 years due to cardiovascular complications [1]. Seropositive RA is linked to the *HLA-DRB1* high risk allele, and is associated with the presence of rheumatoid factor (RF) and/or anti-citrullinated peptide antibodies (ACPA). *HLA-DRB1* alleles share a common motif called the “shared susceptibility epitope (SE)”. The SE accommodates self-epitopes for presentation by antigen presenting dendritic cells (DCs) to the immune system [2-4]. HLA alleles associated with ACPA-positive RA, include HLA-DRB1*04:01 and *01:01. In the immediate pre-RA period, ACPA isotype diversity and titre have been shown to increase – a process associated with antigen-specific CD4+ T cell help for affinity maturation of antibody in germinal centres [5]. *HLA-DR SE* are associated with ACPA+ RA rather than presence of ACPA, implying that presentation of Cit-autoantigens bound to HLA-DR SE molecules to CD4+ T cells is associated with diversification and amplification of ACPA as well as RA development in at-risk individuals carrying *HLA-DR SE*.

Collagen type II (CII) is exclusively expressed in articular cartilage. Mice, rats and monkeys immunized with bovine, chick or human CII develop collagen-induced arthritis (CIA). CII-specific autoreactive CD4 T cells and B cells have been demonstrated in mice and humans. The dominant T cell epitope (CII₂₅₉₋₂₇₃) has been elucidated in HLA-DRB1*04:01 and HLA-DRB1*01:01 transgenic (TG) mice immunized with bovine or human CII [6, 7]. The minimal T cell epitope is mapped to positions 262-270 [8]. Phenylalanine 263 and the negatively charged glutamate 266 provide strong anchors at specific sites in the HLA-DR-SE binding site [7]. T cells from DRB1*04:01+ RA patients have been shown to respond to the dominant collagen II epitope as well as post-translationally modified epitopes [9]. In HLA-DR4 TG mice, the native rather than glycosylated CII epitope was immunodominant [6]. We have demonstrated collagen II peptide-specific CD4+ T cells in peripheral blood (PB) of DRB1*04:01+ and DRB1*01:01+ RA patients, first-degree relatives and healthy controls, using specific major histocompatibility type II (MHC II) tetramer staining reagents.

Multiple forms of CII tolerising immunotherapy have been demonstrated to suppress disease severity and T cell responses in H-2q, DR1-TG and DR4-TG mice, including tolerogenic DCs and collagen₂₅₉₋₂₇₃-HLA-DR4 coated nanoparticles [10-12]. CII-specific autoantibodies are directly pathogenic upon transfer to mice [13]. This occurs through complement fixation and direct binding of the autoantibodies to articular cartilage, leading to a local inflammatory response which models the effector phase of autoimmune arthritis. Autoantibodies recognizing an immunodominant conformational epitope known as C1^{III} (residues 359-369) were significantly elevated in early RA patients compared to healthy controls, and titres were higher in HLA-DR-SE patients [14].

In summary, the development of ACPA+ RA in individuals carrying a specific set of high-risk HLA-DR alleles, the identification of dominant self-epitopes binding to and presented to T cells by those HLA-DR molecules, and their role in RA autoimmune pathogenesis sets the stage to specifically modulate the immune response towards immunodominant self-epitopes in favour of tolerance using antigen-specific tolerance strategies.

3.2 DEN-181 – An Antigen-specific Tolerance Strategy

Current treatments to control pathological immune responses during autoimmunity use broadly immunosuppressive drugs which can be associated with undesirable side effects. Alternative strategies to induce antigen-specific immunological tolerance to control both cellular and humoral immune responses are desirable.

DEN-181

Dendright Pty Ltd

Antigen-directed immunomodulation of antigen-presenting cells to induce immune regulation has previously been evaluated in the setting of RA. In a phase 1 clinical trial, the safety and immune effects of intradermally-injected autologous DCs, modified ex vivo through exposure to an NF- κ B inhibitor and citrullinated peptides were assessed. This treatment reduced circulating effector T cells and increased the ratio of regulatory to effector T cells in RA [15].

To simplify and operationalise antigen-directed immunomodulation, Dendright has developed a strategy for passive targeting of antigen presenting cells (APC) in situ after systemically administering a nanoparticle-based immunotherapy (DEN-181), which exerts pharmacological effects on target immune cells following uptake. DEN-181 is a subcutaneously administered combination drug product comprising liposomal nanoparticles encapsulating a fixed dose of two biomolecules: (1) 1,25-dihydroxyvitamin D3 (calcitriol), an endogenous vitamin D compound and known inhibitor of NF- κ B activation, and (2) a non-conformational linear peptide corresponding to an RA-associated peptide self-antigen, the 259 - 273 region of human collagen II protein.

The hypothesis which underlies the rationale for DEN-181 therapy is that APC uptake and cellular processing of the active components of DEN-181 will lead to immune modulation/regulation of activated collagen II-specific effector T cells resulting in clinical benefit. Theoretically, DEN-181 should offer higher specificity of effect and lower toxicity than current treatments for RA in HLA-DRB*0401+ and *0101+ individuals, given the lack of broadly suppressive effects on the immune system. To study the effects of DEN-181 therapy on immune cell populations, tetramer-based immune-monitoring assays involving staining, enumeration and phenotypic evaluation of antigen-specific and non-antigen specific cells will be conducted.

Included below is a summary of the preclinical and clinical profile of DEN-181. More detailed information is available in the DEN-181 Investigator's Brochure.

